The DSMB will receive report on the progress, adverse events, safety endpoints, and clinical outcomes at each interim analysis from the PI and the statistician. The first planned interim analyses will occur after 20 (11.1%) subjects have been studied and discharged from the hospital following surgery. At this meeting, the DSMB will evaluate subject recruitment, the documentation of subject data, and the collection and reporting of adverse events, serious adverse events, and safety endpoints. The DSMB will also evaluate any study withdrawals, any adverse events, in-hospital all-cause mortality, and safety outcomes (stroke, TIA, or Q-wave myocardial infarction).

The second planned interim analyses will occur after 100 (50%) subjects have been studied and discharged from the hospital following surgery. At this meeting, the DSMB will evaluate any study withdrawals, any adverse events, in-hospital all-cause mortality, safety outcomes (stroke, TIA, or Q-wave myocardial infarction), and a conditional power analysis implemented by the study statistician. The conditional power analysis will assess the likelihood of rejecting the null hypotheses (for the primary endpoints of Aims 1 and 2) at the study conclusion (N=200), assuming that the effect of intervention is as large or larger than the estimated effect at the second interim analysis (N=100). To do so, the study statistician will compare mock-unblinded data (A vs. B, where it remains unknown if A or B is normoxia or

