We have recruited an experienced and versatile DSMB to help us carefully monitor the safety and efficacy of subject treatment. At either planned interim analysis the DSMB may recommend to continue enrollment and subject study or suspend enrollment and subject study due to safety concerns secondary to study intervention including: increased in-hospital all-cause mortality in subjects randomized to physiologic oxygenation (normoxia) such that the DSMB deems the increase is excessive compared to usual care hyperoxic oxygenation (hyperoxia), increased SAEs deemed "Probably Related" or "Possibly Related" to study intervention in physiologic oxygenation (normoxia) group compared to usual care hyperoxic oxygenation (hyperoxia) group deemed excessive, or increased incidence of stroke, TIA, or Q-wave myocardial infarction in the physiologic oxygenation (normoxia) group compared to usual care hyperoxic oxygenation (hyperoxia) group deemed excessive. The DSMB will require strong statistical evidence, corresponding to a p-value threshold of 0.001, to end the trial early due to safety concerns. The DSMB will not make any recommendations to end the study early due to efficacy or futility.

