Adverse events (AE) will be monitored by the PI and his staff. An AE is defined as any untoward medical occurrence in a subject, not necessarily having a causal relationship with the study. A serious AE (SAE) is defined as any untoward medical occurrence that a) results in death, b) is life-threatening, c) requires inpatient hospitalization or prolongation of existing hospitalization, d) results in persistent or significant disability/incapacity, or e) is a congenital anomaly/birth defect. AEs will be graded as a) Mild (no limitation of usual activities), b) Moderate (some limitation), or c) Severe (inability to carry out usual activities) and attributed according to the relationship to the study drug and/or procedures as a) Not related, b) Unlikely Related, c) Possibly Related, d) Probably Related, or e) Definitely Related. AEs will be submitted to the IRB as per IRB regulation. Specifically, any SAE determined to be possibly, probably, or definitely related to study participation will be reported to the data safety monitoring board (DSMB) and the IRB within 10 working days of the PI's notification of the event (as per IRB standards). Summary reports of any previously unreported SAEs will be reported to the IRB annually and to the DSMB at interim analyses and as requested. These reports will contain the number of SAEs, a description of each SAE, the category of each SAE, and the relationship of each SAE to study participation. Appropriate changes will be made to the consent form as required.

Summary Reports will be submitted to the IRB at least annually and will contain a) The number of adverse events and an explanation of how each event was handled, b) The number of complaints and how each complaint was handled, and c) The number of subject withdrawals and an explanation of why the subject withdrew or was withdrawn.

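### The DSMB's SAE ground for suspending the trial omits definitely related events, although section 8.0 has those events reported to the same board

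*Combined protocol and SAP*

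**What the plan says.** The DSMB part of section 6.0 (Study Procedures) lets the board, at either planned interim analysis, recommend that the trial continue or "suspend enrollment and subject study due to safety concerns secondary to study intervention including" three listed grounds:

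- **Mortality:** "increased in-hospital all-cause mortality in subjects randomized to physiologic oxygenation (normoxia".
- **Related SAEs:** "increased SAEs deemed 'Probably Related' or 'Possibly Related' to study intervention in physiologic oxygenation (normoxia) group".
- **Named events:** "increased incidence of stroke, TIA, or Q-wave myocardial infarction in the physiologic oxygenation (normoxia) group".

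Each ground turns on whether the board deems the increase over usual care excessive. The section then adds: "The DSMB will require strong statistical evidence, corresponding to a p-value threshold of 0.001, to end the trial early due to safety concerns".

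Section 8.0 (Reporting of Adverse Events) sets the attribution scale as "a) Not related, b) Unlikely Related, c) Possibly Related, d) Probably Related, or e) Definitely Related". Its expedited rule is that "any SAE determined to be possibly, probably, or definitely related to study participation will be reported to the data safety monitoring board (DSMB") and to the IRB, within 10 working days of the PI's notification.

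On what the board sees at the first interim analysis, section 6.0 says: "The DSMB will also evaluate any study withdrawals, any adverse events, in-hospital all-cause mortality, and safety outcomes". The descriptions of the later looks also list any adverse events.

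**The concern.** The same attribution scale serves the same committee in two places, and the two lists of related events differ by one level, the top one. Section 6.0 puts the level names in quotation marks, so they read as chosen categories and not as loose shorthand for any related event. Nothing else in the protocol or the analysis plan adds the missing level to the ground.

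Applied literally, the SAE ground behaves oddly: regrading an event from probably to definitely related takes it out of the named comparison. The events affected are those that the other two grounds do not cover. Section 7.0 accepts that the intervention may raise the risk of hypoxemia, and that prolonged, severe hypoxemia may injure cells and organs. A life-threatening intraoperative desaturation, or myocardial injury without a new Q-wave, could be graded definitely related and yet fall under neither the mortality ground nor the named-event ground.

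What is at stake is whether the statistician who builds the SAE tables and the board that reads them count the same events. No endpoint, sample size, alpha level or efficacy analysis is affected.

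**Working it through.** The plan states no figure on this point, so there is nothing to reproduce. The check is a comparison of the texts, followed by an illustration.

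**1. Levels named in each place**

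| Attribution level (section 8.0) | Expedited report to DSMB (8.0) | SAE suspension ground (6.0) |
|---|---|---|
| Not related | no | no |
| Unlikely related | no | no |
| Possibly related | yes | yes |
| Probably related | yes | yes |
| Definitely related | yes | **not named** |

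The reporting rule names 3 of 5 levels and the suspension ground names 2 of 5. The difference, 3 − 2 = 1, is the definitely related level.

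**2. What else could pick up a definitely related SAE**

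- An in-hospital death comes under the mortality ground, whatever its attribution.
- A stroke, TIA or Q-wave infarction comes under the named-event ground, whatever its attribution.
- Any other definitely related SAE comes under no listed ground. It can still be raised as a safety concern that is not listed, because the list opens with *including*.

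**3. What the board sees.** Definitely related SAEs reach it within 10 working days. Previously unreported SAEs reach it at interim analyses with their attribution. Its interim review of adverse events has no attribution filter. The gap is in the named comparison, not in the information.

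**4. Could one omitted subject matter?** The documents give no expected number of definitely related SAEs and no test for the 0.001 threshold. That threshold applies to ending the trial early and is not tied to any attribution level. As assumptions, take 50 subjects per arm at the 100-subject look, a two-sided Fisher's exact test, and hypothetical counts of subjects with related SAEs (physiologic vs usual care). With equal arms and no control events, p = 2 × C(50,k)/C(100,k) for k events.

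| Counts | p | Against 0.001 |
|---|---|---|
| 11 vs 0 | 0.0005 | meets |
| 10 vs 0 (one subject omitted) | 0.0012 | does not meet |
| 13 vs 1 | 0.0008 | meets |
| 12 vs 1 (one subject omitted) | 0.0018 | does not meet |
| 6 vs 2 | 0.27 | does not meet |
| 4 vs 2 (two subjects omitted) | 0.68 | does not meet |

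Omitting a single subject can move a result across the threshold, but only when the imbalance is already extreme. At modest counts such as 6 vs 2, the omission lowers the count and does not change the result against 0.001.

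**The case against.** A reader might infer that definitely related SAEs do not count toward pausing the trial, or that the harm rule weakens mechanically as causation becomes clearer. The documents do not support that, for four reasons.

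- The grounds are introduced by *including*, so they are examples. An SAE judged definitely caused by the intervention is plainly a safety concern secondary to it.
- No mechanical tally exists. Each ground rests on the board's judgement that an increase is excessive.
- The board receives these SAEs promptly and reviews all adverse events at its looks.
- Excess death, stroke, TIA and Q-wave infarction count whatever the attribution, which covers much of the severe harm.

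It is also fair to say that the counts in the illustration are hypothetical, and that a sensible board would probably include these events anyway.

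All of this stands, and it limits the consequence. It does not remove the mismatch. An open list admits further grounds, but it does not change the levels written into this one. The ground speaks of relation to the intervention and the reporting rule of relation to study participation. That difference does not explain dropping the strongest level while keeping the weaker two.

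**Conclusion.** The inconsistency is certain on the text: the SAE suspension ground in section 6.0 leaves out the top level of the protocol's own scale, which section 8.0 includes when reporting to the same board. Read literally, a definitely related SAE that is not also an in-hospital death, stroke, TIA or Q-wave infarction is missing from the named between-arm SAE comparison. The board still receives it and may act on it.

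The size is one of three related levels. How many events that means cannot be stated, because the documents give no expected frequency by attribution level.

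A drafting omission is the likely cause, since section 8.0 names the level explicitly for DSMB reporting and no reason for excluding it is given. That is an inference. The point should be treated as an internal-consistency correction to a safety rule, below the level of an essential change.

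**What to change.** Reconcile the DSMB part of section 6.0 with section 8.0. Word the SAE ground to cover SAEs deemed possibly, probably or definitely related, matching the reporting rule. State that the between-arm SAE tables given to the board at every look use the same three levels.

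The cost is a one-line amendment and matching table specifications. No new data are needed, because section 8.0 already has adverse events graded for attribution.

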7.0 Risks

Maintaining physiologic oxygenation during surgery may increase the risk of hypoxemia ($\text{SpO}_2 < 90\%$) compared to delivering hyper-oxygenation. Prolonged and severe hypoxemia ($\text{SpO}_2 < 60\%$ for > 3 minutes) may cause cellular injury, organ infarct, coma, and death. To address any risk of hypoxemia the subject's SpO_2 will be monitored continuously throughout study intervention by an anesthesiologist and/or certified nurse anesthetist. This monitoring is not unique to this study but is current standard of care in North American operating rooms and includes a visual percent readout of the SpO_2 continuously displayed on two large LED monitors in the operating room (one monitor dedicated to the anesthesiologist and one to the operating room surgeon and staff), automated recording of the subject's SpO_2 in the anesthetic record every minute during the subjects stay in the operating room, and an auditory note that sounds with every beat of the heart whose pitch reflects SpO_2 . If a patient's SpO_2 decreases below 90%, an audio and visual alarm is activated notifying the anesthesiologist. All of this monitoring is standard practice during the administration of any anesthetic at VUMC and has been developed to reduce hypoxemia through multiple layers of safety alarms and checks. All anesthesia staff are thoroughly trained and intimately familiar with oxygenation monitoring during surgery.

8.0 Reporting of Adverse Events or Unanticipated Problems involving Risk to Participants or Others

Adverse events (AE) will be monitored by the PI and his staff. An AE is defined as any untoward medical occurrence in a subject, not necessarily having a causal relationship with the study. A serious AE (SAE) is defined as any untoward medical occurrence that a) results in death, b) is life-threatening, c) requires inpatient hospitalization or prolongation of existing hospitalization, d) results in persistent or significant disability/incapacity, or e) is a congenital anomaly/birth defect. AEs will be graded as a) Mild (no limitation of usual activities), b) Moderate (some limitation), or c) Severe (inability to carry out usual activities) and attributed according to the relationship to the study drug and/or procedures as a) Not related, b) Unlikely Related, c) Possibly Related, d) Probably Related, or e) Definitely Related. AEs will be submitted to the IRB as per IRB regulation. Specifically, any SAE determined to be possibly, probably, or definitely related to study participation will be reported to the data safety monitoring board (DSMB) and the IRB within 10 working days of the PI's notification of the event (as per IRB standards). Summary reports of any previously unreported SAEs will be reported to the IRB annually and to the DSMB at interim analyses and as requested. These reports will contain the number of SAEs, a description of each SAE, the category of each SAE, and the relationship of each SAE to study participation. Appropriate changes will be made to the consent form as required.

Summary Reports will be submitted to the IRB at least annually and will contain a) The number of adverse events and an explanation of how each event was handled, b) The number of complaints and how each complaint was handled, and c) The number of subject withdrawals and an explanation of why the subject withdrew or was withdrawn.

9.0 Study Withdrawal/Discontinuation

Patients that are withdrawn from study participation will cease study-specific oxygen administration and monitoring, and their surgical and postoperative care will proceed as directed by their clinical caregivers.

10.0 Statistical Analysis Plan

The primary objective of the analysis will be to compare the effect of intraoperative oxygenation on oxidative damage and organ injury. The primary endpoint of Aim 1 will be change in serum creatinine from baseline (defined as the most recent creatinine measured prior to surgery) to postoperative day 2. The primary endpoint of Aim 2 will be F₂-isoprostanes/isofurans measured in plasma.

Sample Size Calculations

We calculated the subject sample size based on data from the Vanderbilt Statin AKI Cardiac Surgery RCT (PI: [name]).²⁷ Data from this study indicate that mean serum creatinine concentrations increase 0.08 ± 0.37 mg/dl from baseline to postoperative day 2. We have powered the present randomized clinical trial conservatively, particularly since consensus criteria for AKI diagnosis define AKI as a 0.3 mg/dl rise in serum creatinine from baseline to postoperative day 2.²⁹ With 200 subjects, we will have 80% power to detect a 0.15 ± 0.375 mg/dl difference in serum creatinine between groups, with a type I error rate of 5%. In addition, with 200 subjects we will have 80% power to detect a 20 ± 50 pg/ml difference in plasma F₂-isoprostanes between groups, and we observed that physiologic oxygenation was associated with 35 ± 30 pg/ml less increase in plasma concentrations of F₂-isoprostanes among pilot subjects compared to hyper-oxygenated subjects. To account for a potential dropout rate of 10%, we plan to recruit 222 subjects.

For the endothelial function sub-study, we calculated the sample size based on a prior study of patients administered an oral antioxidant, treatment improved FMD 2.3% more than placebo with a standard deviation of 2.0%.³⁰ With 80 patients, we will have greater than 80% power to detect a 2%

difference in FMD change from baseline to ICU admission between subjects randomized to hyper-oxygenation vs. physiologic oxygenation with a standard deviation of 3.0%, with a type I error rate of 0.05 (primary analysis sub-study Aim 1). We will have 94% power to detect a correlation of 0.2 or greater between intraoperative F₂-isoprostan concentrations and postoperative FMD (primary analysis sub-study Aim 2) with standard deviation of 20 pg/ml F₂I and 10 for regression errors. We will have greater than 80% power to detect a 2% difference in FMD between patients who do and do not develop postoperative delirium in the ICU, assuming a delirium incidence of 23.4% among all ROCS trial subjects, similar to that in the Statin AKI Cardiac Surgery RCT. Sub-study Aims 1 and 2 will be completed with 80 ROCS trial subjects and sub-study Aim 3 with all 200 patients.

Randomization

The study's statistician will be responsible for centralized randomization and subject assignment based on stratification in a permuted block fashion, using a sequence of blocks with sizes either two or four, where the sizes are selected uniformly at random. Randomization will be stratified by chronic kidney disease (defined as stage 3, 4, or 5 CKD [i.e., an eGFR <60 ml/min/1.73m²]) and use of cardiopulmonary bypass during surgery. Thus, there will be four randomization strata. We use the modification of diet in renal disease formula to estimate GFR for randomization stratification. This scheme provides ample subject assignment to all strata.

Data Analysis Plan

Standard graphing and screening techniques will be used to evaluate data quality. Data include patient demographics, baseline and intraoperative clinical characteristics, treatment toxicity and clinical outcomes. Summary statistics of study arms for both numerical and categorical variables will be provided to describe the study sample. Continuous variables will be summarized with the 50th (10th, 25th, 75th, 90th) percentiles, mean and standard deviation, and categorical variables will be summarized with the counts and percentages. For outcomes measured at a single time point, comparisons across randomization groups will be implemented using the Fisher's exact test or Pearson chi-square test for categorical variables, and the Wilcoxon rank sum test or Student T-test for quantitative outcomes, as appropriate. The Clopper-Pearson and Wald methods will be used to construct 95% confidence intervals for the between group effects.

Change in serum creatinine from baseline to postoperative day 2 (Aim 1 primary endpoint) will be compared between normoxia and hyperoxia study groups using the Wilcoxon rank sum test. Plasma concentrations of F₂-isoprostanes and isofurans (Aim 2 primary endpoint) will be compared between normoxia and hyperoxia study groups using a mixed effects regression analysis, adjusting for collection time as a categorical variable (i.e., study phase). This method allows for simultaneous evaluation of multiple correlated measurements per subject, and between-subject heterogeneity in the effects of treatment on markers of oxidative stress. Specifically, we will use a random intercept and random 'slope' for treatment allocation, indexed by study subject. Analysis of the effects of treatment on change in creatinine and on oxidative stress will be repeated separately within randomization strata.

We will evaluate treatment effect on additional markers of AKI (AKI incidence using KDIGO criteria, urine concentrations of NGAL and IGFBP-7/TEMP2, use of dialysis), delirium incidence and duration (diagnosed with CAM-ICU), and myocardial damage (quantified by measuring CK-MB on the morning of the day after surgery) as secondary analyses.

To assess effect of treatment on oxygenation and perfusion we will compare SpO₂, PO₂, cerebral oxygenation, muscle oxygenation, mixed venous hemoglobin saturation, cardiac output, and arterial lactate concentrations between normoxia and hyperoxia groups using mixed effects regression analysis as described above for plasma concentrations of F₂-isoprostanes and isofurans.

We will also compare differences in ROS production, mitochondrial function, atrial fibrillation, stroke, pneumonia, wound infection, time-to-extubation, duration of ICU stay, and in-hospital mortality as well as pain scales, depression data, and neurocognitive function between normoxia and hyperoxia groups as secondary endpoints. We will compare safety endpoints myocardial infarction, transient

ischemic attack, and stroke between treatment groups. Similar to the primary analysis, we will implement logistic, proportional odds and linear regression analyses for binary, ordinal or highly skewed, and continuous outcomes, respectively, using a propensity score adjusted approach, if warranted. Potential impactful covariates included in these models will be specific to each outcome (for example, history of chronic obstructive pulmonary dysfunction would be appropriate covariate for time to extubation analysis).

To test the hypothesis (Endothelial function sub-study) that intraoperative physiologic oxygenation improves postoperative endothelial function (sub-study Aim 1) we will compare change from baseline in FMD (primary endpoint of Endothelial function sub-study), reactive hyperemia index, PAI-1, and E-selectin and the amplitude of endothelium-dependent vasodilation randomized subject groups in the first 80 subjects to complete the ROCS trial. The change from baseline in FMD, RHI, PAI-1, and E-selectin and the amplitude of endothelium-dependent vasodilation will be compared between oxygenation groups using Student's t-test or Mann Whitney U test. To test the hypothesis that endothelial dysfunction correlates with increased oxidative stress during cardiac surgery (sub-study Aim 2) we will compare perioperative concentrations of F₂-isoprostanes and isofurans to endothelial function assessments and plasma markers of endothelial activation at ICU admission in the first 80 subjects to complete the ROCS trial using linear regression and adjust for baseline measurements of endothelial function, and confounders such as randomized treatment group, blood transfusion, and duration of CPB. To test the hypothesis that perioperative endothelial dysfunction is associated with organ injury (sub-study Aim 3) we will compare baseline, postoperative, and change from baseline FMD, reactive hyperemia index, PAI-1, and E-selectin and the amplitude of endothelium-dependent vasodilation to markers of AKI, delirium, myocardial injury, and additional secondary endpoints using logistic, linear, or proportional odds regression as appropriate in the total cohort (N=200). We will review, interpret, and report results from sub-study Aims 1 and 2 based on statistical report from [name] but will remain blinded to treatment assignments in these 80 subjects until the entire 200 patient cohort is completed.

Every effort will be made to avoid missing data. Any methods of missing data imputation (e.g. multiple imputation using the chained-equations method) will be used cautiously as sensitivity analyses; and the analysis of results with imputation would be interpreted in the context of corroboration with the analyses without imputation. The primary analysis will be intention-to-treat. Before data unblinding, [name] will examine any protocol deviations and identify a list of protocol violators. In addition to the intention-to-treat analysis, a secondary per-protocol analysis will be conducted.

Specific inferences on the effects of interest will be made by reporting point estimates, along with 95% confidence intervals. Hypotheses will be tested at a two-sided significance level of $\alpha=0.05$. This data analysis plan will be carried out using the statistical analysis package R (R Development Core Team).

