hyperoxia). If the conditional power is less than the original target (80%), the DSMB will consider recommending an increase in the study sample size to achieve the target power. If an increased sample size is determined to be reasonable by the investigators within the study constraints including feasibility and funding, we will seek approval from the VU IRB to increase the sample size. If the sample size is increased based on the conditional power analysis, an additional interim analysis will be scheduled to occur after 200 subjects have been studied and discharged from the hospital after surgery. At this interim analysis meeting (N=200), the DSMB will evaluate safety by analyzing any study withdrawals, any adverse events, in-hospital all-cause mortality, safety outcomes (stroke, TIA, or Q-wave myocardial infarction), and the unblinded treatment effect on the primary endpoint of Aim 1 (previously only assessed in a mock-unblinded manner for the purpose of conditional power analysis). This analysis will be completed to assess safety not efficacy of the intervention. However, if the sample size is increased, then the statistical significance thresholds for the final analyses will be adjusted to preserve the overall type-I error rate at 5%. For example, if the sample size is increased to 300, then the p-value threshold at the final analysis (for the primary aim using the Wilcoxon rank sum test) will be 0.0499 to preserve the overall type-I error probability at 5%.

There will be no possibility of ending the trial early due to futility or efficacy. All investigators and research personnel (other than the study statistician at the second interim analysis) will remain blinded to treatment assignment during all interim analyses.

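### The Aim 2 primary endpoint names two markers, each testable at 0.05, with no rule on whether one or both must be significant; if either suffices, the Aim 2 error is about 7-10%, not 5%

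*Combined protocol and SAP*

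**What the plan says.** Each aim has its own primary endpoint. For Aim 1 it is one variable with one test: "Change in serum creatinine from baseline to postoperative day 2 (Aim 1 primary endpoint) will be compared" by the Wilcoxon rank sum test (section 10.0, Data Analysis Plan). For Aim 2, the sentence in section 10.0 that begins "The primary endpoint of Aim 2 will be" goes on to name two plasma markers, F2-isoprostanes and isofurans, joined by a slash. The Data Analysis Plan then says: "Plasma concentrations of F₂-isoprostanes and isofurans (Aim 2 primary endpoint) will be compared" by mixed effects regression, with collection time as a categorical covariate and, per subject, a random intercept and a random treatment slope.

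On error rates, section 10.0 says: "Hypotheses will be tested at a two-sided significance level of" 0.05. The sample size paragraph gives 80% power with 200 subjects for creatinine (0.15 ± 0.375 mg/dl) and for F2-isoprostanes (20 ± 50 pg/ml). Isofurans have no effect size, standard deviation or power.

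Section 6.0 (Data and Safety Monitoring Board) plans a conditional power analysis at 100 subjects for the primary endpoints of both aims. A value below 80% may lead to a larger sample. For that contingency alone it says: "then the statistical significance thresholds for the final analyses will be adjusted to preserve the overall type-I error rate at 5"%. The example given is a final threshold of 0.0499 for the Wilcoxon test of the primary aim at 300 subjects.

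**The concern.** A primary endpoint made of two measurements needs a decision rule: either one suffices, both are required, they are tested in order, or they are combined. The plan has none for Aim 2. If the two results differ, Aim 2 could be called positive on whichever marker is significant, and a reader could not tell whether that rule was set in advance.

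A split result is realistic. Section 2.0 says that high oxygen tension favours the formation of isofurans over F2-isoprostanes, and that isofurans rise more during cardiac surgery. The trial manipulates oxygen tension, so the two markers may well respond differently.

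The gap also affects the conduct of the trial. The statistician cannot compute one conditional power for Aim 2 at 100 subjects without knowing which marker, or which combination, defines rejection, and that figure can prompt a sample size increase.

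**Working it through.** **1. The plan's own power figure.** Inputs from section 10.0: difference 20 and SD 50 pg/ml (ratio 0.4), two-sided alpha 0.05, 200 subjects. Equal allocation is assumed, as two arms with blocks of two or four imply.
- Per arm: 2 × (1.960 + 0.842)² / 0.4² = 98.1, rounded up to 99.
- Power at 100 per arm: Φ(0.4 / √(2/100) − 1.960) = Φ(2.828 − 1.960) = 80.7% (80.4% by t-test).

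The stated 80% is reproduced for F2-isoprostanes as a single test at 0.05. Creatinine has the same ratio (0.15/0.375 = 0.4) and gives the same result. No such check is possible for isofurans.

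**2. One test or two?** The terms listed for the Aim 2 model are treatment, collection time, and a subject-level intercept and treatment slope. There is no marker term, composite score or joint test. The model therefore applies to one marker at a time, giving two tests, each at 0.05 under the general rule.

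**3. Aim 2 error if either marker suffices.** Assume that treatment affects neither marker. With test statistics Z1 and Z2 and correlation ρ, the error is 1 − P(|Z1| < 1.96 and |Z2| < 1.96). For ρ = 0 this is 1 − 0.95² = 9.75%. Otherwise it comes from the bivariate normal distribution. The documents give no correlation, so a range is shown.

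| Assumed ρ | Either marker suffices | Both required |
|---|---|---|
| 0 | 9.75% | 0.25% |
| 0.3 | 9.5% | 0.5% |
| 0.5 | 9.1% | 0.9% |
| 0.7 | 8.3% | 1.7% |
| 0.9 | 7.0% | 3.0% |

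The last column is 5% + 5% minus the middle column. If treatment affects one marker and not the other, the error of a both-required rule can rise to 5% but no further. Its power cannot exceed that of the weaker marker, and for isofurans that power is not stated.

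**4. What 0.0499 corrects for.** Suppose one look at the Aim 1 test at 200 of 300 subjects, at the 0.001 threshold that section 6.0 gives for stopping on safety grounds. The correlation between the look and the final test is √(200/300) = 0.816. Solving for a total error of 5% gives a final threshold of 0.04994, which rounds to 0.0499. The documents do not show this derivation, but the figure fits a correction for one extra look at one endpoint, with no allowance for several endpoints.

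**The case against.** The strongest defence is that the documents word Aim 2 as one endpoint and nowhere say that either marker alone establishes it. If both were required, the Aim 2 error would be at most 5%. That stands: the defect is a missing rule, and the inflation follows only under one of the readings left open. The two markers are also unlikely to be independent, since both are products of arachidonic acid peroxidation, so 9.75% is the upper end. The consequence is moderate too: section 2.0 says positive findings would lead to multicenter validation, and section 10.0 reports estimates with 95% confidence intervals.

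Two stronger readings are tempting but not supported.
- A reader might take the wording "to preserve the overall type-I error probability at 5"% as a promise covering all primary endpoints, and so see a contradiction. The sentence applies only if the sample size is increased, it concerns the added look, and its only example is the single Wilcoxon test. The documents make no unconditional claim of 5% across endpoints.
- A reader might pool all three tests and call 1 − 0.95³ = 14.3% the trial's real error rate, or 1 − 0.95² = 9.75% for one test per aim. That requires independence, no effect on any endpoint, and a single success claim shared by both aims. The aims ask different questions with their own hypotheses, and 5% per aim is defensible. Section 2.0 does allow a finding on either oxidative stress or organ injury to prompt further studies, but a trigger for follow-on research is not a trial-wide success criterion.

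A last objection is to the remedy: placing isofurans second demotes the marker that section 2.0 links more closely to oxygen tension. That is a real cost. Against it, F2-isoprostanes is the only marker for which the plan states power.

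**Conclusion.** The concern holds for Aim 2 only. Two markers form its primary endpoint, the model described treats them one at a time at two-sided 0.05, and no rule says what counts as success. If either marker is enough, the Aim 2 error is about 7-10% in place of 5%: 9.75% if independent, 8.3% at a correlation of 0.7, and 7.0% at 0.9. The figures assume no treatment effect on either marker and correlations that the documents do not give. The absence of a defined target for the Aim 2 conditional power rests on none of these assumptions. Aim 1 is unaffected: it has one endpoint, one test and reproducible power.

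**What to change.** Amend section 10.0, and the matching endpoint entry in section 6.0, as follows.
- Name plasma F2-isoprostanes as the single Aim 2 primary endpoint, and use it for the Aim 2 conditional power at 100 subjects.
- Make isofurans the first secondary endpoint of Aim 2, tested at two-sided 0.05 only if F2-isoprostanes is significant. Otherwise report the estimate and confidence interval without a claim.
- State that the 5% level applies separately to each aim.
- State in section 6.0 that the 0.0499 example corrects only for the added interim look at the Aim 1 test.

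The ordering holds Aim 2 at 5% whatever the correlation: if F2-isoprostanes is unaffected, any false claim must begin with a 5% event; if it is affected, the only possible false claim is the single isofurans test. No ordering between Aim 1 and Aim 2 is needed. It would block the oxidative stress test whenever creatinine is not significant, which at 80% power happens about 20% of the time even if the design effect is true.

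The cost is a few sentences, with no added patients and no loss of the stated 80% power. The downside is that isofurans can no longer establish Aim 2 alone. The change should be made before any comparison by group, and so before the analysis at 100 subjects.
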